2.4. Sample size estimate

By using G*Power (Faul et al., 2009) calculation, according to Kurtz et al. (2013), the effect size is 0.53 for a behavioural intervention for High Risk Substance-Using MSM.

[figure not shown]

Figure 1. G-Power calculation

t tests - Means: Difference between two independent means (two groups)

Analysis: A priori: Compute required sample size

Input: Tail(s) = Two

Effect size d = 0.53 α err prob = 0.05Power (1- β err prob) = 0.95Allocation ratio N2/N1 = 1

Output: Noncentrality parameter $\delta = 3.6334969$

Critical t = 1.9728001

Df = 186 Sample size group 1 = 94 Sample size group 2 = 94 Total sample size = 188

Actual power = 0.9510082

A sample of 94 participants per condition was needed to detect a differential impact of the intervention compared to the control condition at the 6-week and 12-week follow-up. A 20% attrition rate was allowed for, leading to a targeted sample size of 226 participants.

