Study Protocol

The development of an online intervention to reduce HIV/STI risk and drug use-related harms among stimulant-using MSM in Malaysia

Version 2.1 08/03/2022

Planned Study Period: 1 December 2020 – 30 June 2022

Sponsor : Malaysian AIDS Council

Funders : Global Fund to Fight AIDS, Tuberculosis and Malaria

Sustainability of HIV Services for Key Populations in Asia Program

(SKPA)

Investigators : [name]

Department of Social and Preventive Medicine,

Faculty of Medicine, University of Malaya.

Associate [name] [name]

Department of Psychological Medicine,

Faculty of Medicine, University of Malaya.

ISTCTN : 14406171

Study Synopsis

Study title	The development of an online intervention to reduce HIV/STI risk and
	drug use-related harms among stimulant-using men who have sex with men (MSM) in Malaysia
Sponsor	Malaysian AIDS Council
Funder	Global Fund to Fight AIDS, Tuberculosis and Malaria
Tunder	Sustainability of HIV Services for Key Populations in Asia Program (SKPA)
ISRCTN	14406171
Project Start Date	December 2020
Project End Date	June 2022
Research Aspect	The study will develop a community-based, online intervention to cater
1	the mental health and sexual health needs for stimulant-using MSM in Malaysia. Participants are able to access harm-reduction information, support for drug use recovery, as well as peer counselling on sexual risk reduction at their own privacy and convenient time. The study builds the capacity of community-based organization in reaching stimulant-using MSM and provide evidence-based, psychosocial support to these men who are vulnerable to a range of adverse health outcomes, including depression, suicidality, HIV/STI/Hepatitis C & B Infection.
Objectives	To develop an online intervention for stimulant-using MSM in Malaysia
3	and collect feasibility and efficacy data
Study Design	Randomized control trial.
Sample Size	226 men aged at least 18 years who eEngaged in chemsex with other men (defined as using crystal methamphetamine, GBL/GHB, or ecstasy/MDMA) in the past 12 months
Intervention and	Participants will be randomly allocated to two groups:
control groups	, , , , , , , , , , , , , , , , , , ,

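### The 20% attrition allowance was applied as 188 × 1.20, so 226 enrolled leaves about 181 completers, not the 188 behind the 95% power figure (minor)

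*Protocol*

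**What the plan says.** Protocol Section 2.4 (Sample size estimate) sets out a G*Power calculation. The test is "t tests - Means: Difference between two independent means (two groups", two-sided, with alpha 0.05, target power 0.95 and 1:1 allocation. The effect size is taken from a cited trial: "the effect size is 0.53 for a behavioural intervention for High Risk Substance-Using MSM". The output is "Sample size group 1 = 94 Sample size group 2 = 94 Total sample size = 188", with "Actual power = 0.9510082".

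The section then presents 94 per condition as the number needed to show a difference at the 6-week and 12-week follow-up, and closes with the allowance for loss: "A 20% attrition rate was allowed for, leading to a targeted sample size of 226 participants". It does not print the inflation formula.

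The synopsis repeats the target only as a number of men to be enrolled ("226 men aged at least 18 years who eEngaged in chemsex with other men"), with no attrition rate and no power figure.

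**The concern.** Because the 94 per condition are needed at follow-up, the 188 are completers, and the allowance exists to protect that number. An attrition rate is ordinarily the fraction of enrolled participants who are lost. If 20% of those enrolled are lost, the enrolled number times 0.80 must be at least 188. A target of 226 does not meet that condition.

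At stake is the truth of a headline design statement. The section combines 20% attrition, 94 evaluable per arm, 95% power and a target of 226, and these four cannot all hold together. A trial report is likely to repeat the sentence, and a reader can check it in one line.

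**Working it through.** **Inputs, all from Protocol Section 2.4:** two-sample t test, two-sided, alpha 0.05, d = 0.53, target power 0.95, 1:1 allocation, 94 per arm (188 in total), attrition 20%, target 226.

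**Step 1: reproduce the protocol's power figure.** With n1 and n2 per arm, the noncentrality parameter is δ = d × √(n1·n2 / (n1 + n2)), with n1 + n2 − 2 degrees of freedom. For 94 per arm, δ = 0.53 × √47 = 3.6335, df = 186, critical t = 1.9728 and power = 0.9510. All four match the printed output. At 93 per arm power is 0.9490, so 94 is the smallest group size that reaches 0.95. The starting point is sound.

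**Step 2: reproduce 226.**
- Multiplying: 188 × 1.20 = 225.6, rounded up to 226. Per arm, 94 × 1.20 = 112.8, rounded up to 113, and 2 × 113 = 226. This is the stated target.
- Dividing: 188 / (1 − 0.20) = 235. Per arm, 94 / 0.80 = 117.5, rounded up to 118, and 2 × 118 = 236. This is 9 or 10 more than stated.

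Of the two usual formulas, only the multiplication gives 226.

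**Step 3: what 226 leaves at 20% attrition.** 226 × 0.80 = 180.8, or 90.4 per arm. That is 188 − 180.8 = 7.2 short, so 7 to 8 completers.

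**Step 4: power with those completers** (same t test, d = 0.53):

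| Completers per arm | Power |
|---|---|
| 94 / 94 (as planned) | 0.9510 |
| 91 / 91 | 0.9447 |
| 90 / 91 | 0.9436 |
| 90 / 90 | 0.9425 |

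The loss is 0.6 to 0.9 percentage points. With 90 and 91 completers, the d detectable at 95% power is 0.539.

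**Step 5: the attrition that 226 does absorb.** (226 − 188) / 226 = 38 / 226 = 16.8%.

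**The case against.** **The effect is negligible.** This stands. The shortfall is worth about 0.01 in an effect size borrowed from another trial and quoted to two decimals. At d = 0.525 the same calculation asks for 96 per arm, at 0.535 for 92 and at 0.54 for 91; with 90 and 91 completers, power at d = 0.54 is 0.951. The protocol also calls the trial a pilot that collects feasibility and preliminary efficacy data. A reader might infer that the trial is underpowered. The figures do not support that: about 94% against a self-chosen 95% is not a threat to the trial.

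**The planned analysis is not a t test on completers.** Section 2.4.2 plans mixed models using all available data, with missing data handled by maximum likelihood. Two things follow.

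- This does not supply the missing completers. Section 2.4.1 measures the primary outcome, eASSIST, only at baseline and 12 weeks, so a participant lost before week 12 has no primary value after baseline.
- The power of the model that will be fitted depends on the correlation between baseline and week 12, which the protocol does not give. Assume that d = 0.53 is on the follow-up SD and that there are 90 and 91 completers. A baseline-adjusted contrast, with effective d = 0.53 / √(1 − ρ²), has power 0.951 at ρ = 0.19 and 0.984 at ρ = 0.5. A change-score contrast, with effective d = 0.53 / √(2(1 − ρ)), has power 0.899 at ρ = 0.4, 0.944 at 0.5 and 0.977 at 0.6. The correlation can move power further than the inflation formula does, and for the change score in either direction. So 94.3% and 0.539 must be labelled as planning t-test figures. The protocol states its power on that test alone, and on that basis the sentence is wrong.

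**The 20% could be meant as a mark-up on 188.** No formula is printed, so this is possible arithmetically. But the text calls it an attrition rate, and the rate that 226 accommodates is 16.8%.

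**The synopsis repeats 226.** A reader might infer that the error extends there. It does not: the synopsis makes no attrition or power claim, so 226 stands as the enrolment target.

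**Conclusion.** The point holds as a minor error of arithmetic confined to one sentence in Section 2.4. The allowance was added to the completers instead of being taken from the enrolled. At the protocol's own 20% attrition, 226 leaves about 181 completers, 7 to 8 fewer than the 188 stated as needed, and power for the planning t test is about 94.3% instead of 95.1%.

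This rests on reading the 188 as completers, which the reference to follow-up supports, on attrition meaning the share of enrolled participants lost, and on losses being about equal in the two arms. It says nothing about the power of the mixed model. It does not affect the choice of outcome or the analysis, and it does not by itself require more participants.

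**What to change.** Keep 226 and correct the one sentence in Section 2.4. Either of these is true:

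- 226 enrolled with 20% attrition leaves about 181 participants (about 90 per arm), giving about 94% power for the planning t test at d = 0.53; or
- 226 enrolled allows 16.8% attrition while keeping 188 completers and 95% power for that test.

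The cost is one reworded sentence and a slightly less favourable power or attrition figure. No participants are added, and the synopsis stays as it is.

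Keeping both 20% and 95% would need 235 enrolled (236 with equal arms). That is open only if recruitment is still running, and time is short: the planned study period ends on 30 June 2022, so a 12-week follow-up implies that enrolment closes around early April 2022. The gain, under one percentage point of power, does not make this route necessary.

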2.4. Data analysis

2.4.1. Outcome variables

The primary outcome variable is the eASSIST (eASSIST; measured at baseline and 12-week follow-up) which indicates stimulant use severity (Gryczynski et al., 2015). The secondary outcome variables, number of days stimulants used in the last 30 days and the Depression, Anxiety and Stress Scale - 21 Items (DASS-21) will be measured at baseline, 6-week and 12-week follow-up. Among HIV-negative participants, willingness to access PrEP and utilization of PrEP will be assessed while among HIV-positive participants, linkage to HIV services and adherence to ART will be assessed at the 12-week follow up. Additionally, data on utilization of HIV/STI services at the community-friendly clinics will be extracted from the HIV/STI monitoring database by Malaysian AIDS Council using the unique client ID.

2.4.2. Analysis plan

Bivariate comparisons of baseline demographic and outcome variables will be conducted. Outcome analyses will employ mixed effect repeated measures outcomes and used all available data for each time point. Overall, 3 separate mixed-effect models will be conducted to examine the effect of time, intervention condition, and the time by intervention condition on each outcome variable. Missing data will be analysed using a maximum likelihood approach.

[figure not shown]

Figure 2. Study Flowchart

3. Online Intervention

The online intervention will comprise two components: 1) **Brief Intervention (FRAME model)** to be administered by case workers online, and 2) **Chemsex care Plan**, a self-directed, interactive online material that participants can access anytime, at their convenience.

[figure not shown]

Figure 3. Online intervention flow chart

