	Group A (Intervention Group Group A will receive the developed intervention tool comprising a Brief Intervention (FRAME Model). An online meeting will be arranged with a trained, peer counsellor to discuss drug use behaviour and to provide support and motivation to change. After the brief counseling, participant will then be directed to the Chemsex Care Plan, a self-directed interactive program that participants can access anytime at their convenience and will provide participants access to online materials (videos, infographics, etc) to educate stimulant-using MSM on reducing risky drug-use behaviour, as well as goal-setting. Participant will be asked to complete a brief survey at 6-week and 12-week follow-up to assess the drug use behavior and motivation to change.
	Group B (Control Group) Group B will receive a self-help toolkit from the World Health Organization for cutting down and stopping drug use. Participant is encouraged to use the toolkit to manage their drug use for 12 weeks. Similar to Group A, they will then be asked to complete a follow-up survey after 6 weeks and 12 weeks. After the end of the study, they will be given access to the Chemsex Care Plan.

	Randomization							
	Participants who agree to the follow-up study are sent a link and a							
	password (unique password for each participant) to log onto the study							
	website. Those logging on are randomized in 1:1 ratio with no							
	stratification to receive their respective materials.							
Study outcomes	The development of the online intervention addresses the worsening HIV							
	epidemic in a subpopulation of MSM in Malaysia. This pilot study							
	collects the feasibility, acceptability, and preliminary efficacy of ASSIT-							
	Brief Intervention and Chemsex Care Plan to reduce harms related to							
	drug use and sexual risk among MSM.							
Measurements	Primary outcome measure							
	Stimulant use severity is measured using e-ASSIST (eASSIST; measured							
	at baseline and 12-week follow-up)							
	- /							
	Secondary outcome measures							
	Measured at baseline, 6-week, and 12-week follow-up:							
	1. Number of days stimulants used in the last 30 days							
	2. Depression, Anxiety, and Stress Scale - 21 Items (DASS-21)							

Project Summary

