3.1 Brief Intervention (FRAMES model)

Participants will be asked to schedule an appointment to interact virtually with the case workers from the NGO to receive brief intervention after completing eASSIST. A personal chatroom will be opened for the case worker and participants to enhance anonymity and privacy. Participants may request video conference when they feel comfortable to do so. Following the screening questions from e-ASSIST, the case workers or peer counsellor will provide brief intervention (BI) which included the discussion of the scores of the eASSIST Feedback Report card and use of motivational Interviewing (MI) techniques to assess and motivate clients to change drug use behaviors. The principles underlying most approaches to BI were systemized by Miller and Sanchez (1994) in a FRAMES model which comprised of:

- Feedback: Give feedback on the risks and negative consequences of substance use.
- **Responsibility**: Emphasize that the individual is responsible for making his or her own decision about his/her drug use.
- Advice: Give straightforward advice on modifying drug use.
- **Menu of options**: Give menus of options to choose from, fostering the client's involvement in decision-making.
- Empathy: Be empathic, respectful, and non-judgmental.
- **Self-efficacy**: Express optimism that the individual can modify his or her substance use if they choose. Self-efficacy is one's ability to produce a desired result or effect.

The eASSIST-linked BI aimed at reducing illicit substance use and related risks is shown to be effective in different countries (Humeniuk et al., 2012). The brief intervention is based on the approach of motivational interviewing, which is a directive, client-centered counselling method developed from experience of alcoholism treatment by Miller. Several randomized clinical trials showed that MI is effective for reducing alcohol and substance use in general populations as well as in MSM (Morgenstern J 2009, William Zule 2012, Parson et al. 2014, Parson et al. 2018). Furthermore, MI is listed as one of the best behavioural interventions for HIV risk reduction by the US Centers for Disease Control and Prevention, http://www.cdc.gov/hiv/topics/research/prs/best-evidence-intervention,htm).

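### Counsellors deliver treatment in Group A only, but the sample size assumes independent men and the described models name no counsellor term; if outcomes vary by counsellor, the 95% power is too high and standard errors too small

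*Protocol*

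**What the plan says.** - **Delivery in Group A.** The Study Synopsis says of the intervention group: "An online meeting will be arranged with a trained, peer counsellor to discuss drug use behaviour". Section 3.1 repeats that "the case workers or peer counsellor will provide brief intervention (BI") after the eASSIST screening. The session lasts about 20 minutes and is followed by the self-directed Chemsex Care Plan.
- **Delivery in Group B.** The Synopsis and section 2.3 give the control men a WHO self-help toolkit. No counsellor is involved.
- **Sample size.** The section headed Sample size estimate uses "t tests - Means: Difference between two independent means (two groups"), with "Effect size d = 0.53 α err prob = 0.05Power (1- β err prob) = 0.95Allocation ratio N2/N1 = 1" and the output "Df = 186 Sample size group 1 = 94 Sample size group 2 = 94 Total sample size = 188". It has no design effect, ICC or caseload.
- **Analysis.** Section 2.4.2 says "Outcome analyses will employ mixed effect repeated measures outcomes and used all available data for each time point". It describes three models that examine time, condition and the time-by-condition interaction. No counsellor effect is mentioned.
- **Number of counsellors.** None is given. Section 5 describes the training and certification of case workers but not how many there will be or how many men each will see.

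**The concern.** This is a partially nested design. Group A men who share a counsellor also share that person's skill and style, while Group B men share nothing comparable. The random effects of a repeated-measures model deal with several measurements on one man. They do not deal with several men under one counsellor.

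If outcomes differ between counsellors, the Group A mean carries an extra variance component that averages out over counsellors, not over men. A standard error built on independent men omits it. Two things are then at stake for the primary comparison: an interval that is too narrow for conclusions about this intervention in other counsellors' hands, and a power figure that is too high.

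The protocol itself allows that delivery may vary. Section 4 plans audio recording to check that case workers follow the protocol, and section 5 certifies only those who qualify.

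**Working it through.** **Inputs from the protocol:** d = 0.53, two-sided alpha 0.05, 94 completers per arm, stated power 0.951.

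**Inputs assumed, because the protocol gives none:** k counsellors with equal caseloads m = 94/k, an ICC, total variance 1 in both arms, and every Group A man meeting a counsellor. The 12-week contrast is treated as a comparison of two means, as in the protocol's own calculation.

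**Step 1, the protocol's figure.** The noncentrality is 0.53 × √(94/2) = 3.633. On 186 degrees of freedom the critical t is 1.973 and power is 0.951. The stated result is reproduced exactly under independence.

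**Step 2, variance under nesting.** The design effect in Group A is DE = 1 + (m − 1) × ICC; in Group B it is 1. Hence SE² = (DE + 1)/94, against 2/94 under independence. The true SE exceeds the independence SE by the factor r = √[(DE + 1)/2].

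**Step 3, type I error of the independence analysis when the average effect is zero.** This is 2 × [1 − Φ(1.96/r)].

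**Step 4, power of an analysis that allows for counsellors.** The noncentrality is 0.53/SE, on Satterthwaite degrees of freedom df = (v₁ + v₀)² / [v₁²/(k − 1) + v₀²/93], where v₁ = DE/94 and v₀ = 1/94.

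Worked case, k = 5 and ICC 0.05:
- m = 94/5 = 18.8 and DE = 1 + 17.8 × 0.05 = 1.89.
- r = √(2.89/2) = √1.445 = 1.202.
- Type I error = 2 × [1 − Φ(1.96/1.202)] = 2 × [1 − Φ(1.63)] = 0.103.
- SE = √(2.89/94) = 0.175, noncentrality 0.53/0.175 = 3.02, df = 9.2, critical t = 2.253, power 0.77.
- Interval width relative to the independence analysis: 1.202 × 2.253/1.973 = 1.37.

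| k | ICC | m | DE | r | Type I error | df | Power | Interval wider by |
|---|---|---|---|---|---|---|---|---|
| 20 | 0.01 | 4.7 | 1.037 | 1.009 | 0.052 | 62 | 0.94 | 2% |
| 10 | 0.02 | 9.4 | 1.168 | 1.041 | 0.060 | 29 | 0.92 | 8% |
| 10 | 0.05 | 9.4 | 1.420 | 1.100 | 0.075 | 25 | 0.89 | 15% |
| 5 | 0.02 | 18.8 | 1.356 | 1.085 | 0.071 | 12 | 0.87 | 20% |
| 5 | 0.05 | 18.8 | 1.890 | 1.202 | 0.103 | 9 | 0.77 | 37% |

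Simulation of the ordinary t test agrees with the type I column: 0.054 for k = 20 and ICC 0.01, about 0.074 for k = 10 and ICC 0.05, and 0.107 for k = 5 and ICC 0.05. At ICC = 0 nothing changes.

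**The case against.** **The driving quantities are not in the protocol.** A reader might infer a small pool of counsellors from the several days of training and certification in section 5. The document does not say so. Nor does it say that standard errors will be too small: that needs shared counsellors and an ICC above zero. This stands, and the point is therefore conditional.

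**The ICC may be low.** There is one session of about 20 minutes, the Care Plan is self-directed, training is common, and recordings are reviewed. The Introduction also offers men who do not want contact with CBO workers a route through the electronic ASSIST to the Care Plan. Such men would reduce the clustering, whereas the working puts all 94 under a counsellor. Against this, section 3.1 has case workers also booking clinic appointments and offering to accompany men, so contact may go beyond the session. Unequal caseloads would generally add to the inflation.

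**Type I error is not inflated under every null.** Men are randomised individually. If the intervention changes nobody's outcome, counsellors cannot create differences and the ordinary test keeps about 5%. Inflation arises when the average effect is zero but counsellors differ, and the inference is to counsellors beyond those used. This stands. The wider target is nonetheless reasonable, because the Project Summary plans integration into NGO services.

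**Bias.** One might read this as counsellor differences being counted as treatment effect. That is not so: the issue is the variance, not the estimate.

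**The model may be completed elsewhere.** Section 2.4.2 lists effects to be examined and need not be the full random-effects structure. A statistical analysis plan that is not shown may add a counsellor term. The model part is therefore the weaker one. The sample size is fixed in the protocol.

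**It is a pilot.** The protocol speaks of preliminary efficacy, which lowers the stakes. It also claims 95% power, and that figure should carry its assumption.

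**Conclusion.** The point holds in conditional form. Treatment is delivered by counsellors in one arm only. The sample size assumes independent men, and the described analysis names no counsellor term. If several men share a counsellor and the ICC is above zero, the 95% power is overstated and the standard error is too small for inference beyond these counsellors.

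The size cannot be fixed from the protocol. Over the assumed range it goes from trivial (20 counsellors, ICC 0.01: type I error 0.052, power 0.94) to material (5 counsellors, ICC 0.05: about 0.10 and 0.77). The type I figures apply to a zero average effect with real differences between counsellors. They do not apply if the intervention affects nobody. The protocol does not support a flat statement that the false-positive rate exceeds 5%.

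**What to change.** 1. Record the counsellor ID for every Group A session. Section 5 already plans to record the duration of peer counselling, so this is one more field. If it is not collected, the nested analysis may not be possible later.
2. Pre-specify, at least as a sensitivity analysis of the primary outcome, a partially nested model: a counsellor random effect in Group A only, with Satterthwaite or Kenward-Roger degrees of freedom. Group A men who meet no counsellor enter as singletons. Whether this should be the primary model is debatable if counsellors are few.
3. State the number of counsellors and the expected caseload. Say in the sample size section that the 95% power assumes independent men, and show power over a range of ICCs and counsellor numbers.

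The cost is one data field, one further analysis and a short table. The downside is a wider interval in that analysis, by about 2% to 37% over the range above, and an imprecise estimate of the counsellor variance if there are few counsellors.

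### The primary efficacy test is not named, and its natural reading, the time-by-condition interaction, is less precise than a baseline-adjusted 12-week comparison

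*Protocol*

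**What the plan says.** The analysis plan (section 2.4.2) specifies three mixed models, one per outcome, to "examine the effect of time, intervention condition, and the time by intervention condition on each outcome variable". They use all available data, and "Missing data will be analysed using a maximum likelihood approach". None of the three effects is identified as the test of efficacy, and nothing says how the baseline score enters the comparison.

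The primary outcome is the eASSIST score, "measured at baseline and 12-week follow-up" (section 2.4.1; the Synopsis agrees). Days of stimulant use and DASS-21 are secondary and are also measured at week 6.

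The section headed Sample size estimate uses a different test: "t tests - Means: Difference between two independent means (two groups"), two-sided, alpha 0.05, power 0.95. Its effect size comes from a cited trial: "the effect size is 0.53 for a behavioural intervention for High Risk Substance-Using MSM". The SD that 0.53 is scaled by is not given. The result is described as follows: "A sample of 94 participants per condition was needed to detect a differential impact of the intervention compared to the control condition at the 6-week"; the same sentence also covers week 12. On dropout, the section adds: "A 20% attrition rate was allowed for, leading to a targeted sample size of 226 participants".

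**The concern.** The sample size rests on a comparison of two means at one time, with no baseline term. The analysis is a model with a free baseline mean in each arm. With only two time points, the interaction in that model is the between-arm difference in change from baseline. Its precision depends on the correlation between the two scores, which the t test ignores. If the correlation is low, subtracting the baseline adds noise, and the planned test can be weaker than the one that was powered. At any correlation below 1, a comparison that adjusts for baseline does better, and section 2.1 already collects the baseline score from everyone.

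The rest of the protocol does not name the test either. The hypothesis in section 5 speaks of a decrease from baseline among intervention participants, which is a within-arm statement. At stake are a single pre-stated primary test and a gain in precision that costs nothing.

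**Working it through.** **Inputs from the protocol (Sample size estimate).** d = 0.53, two-sided alpha 0.05, 94 per arm, 226 randomised (113 per arm).

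**Assumptions, not in the protocol.** rho, the correlation of baseline and 12-week eASSIST scores, shown from 0.3 to 0.7; equal SDs at both times; 0.53 standardised on the 12-week SD.

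**Step 1: reproduce the plan's figure.** Noncentrality = 0.53 × sqrt(94/2) = 3.6335; df = 186; critical t = 1.9728. The noncentral t distribution gives power 0.9510, as stated.

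**Step 2: variances, taking the 12-week SD as 1.**
- 12-week score alone (the powered t test): 1
- Change score (the interaction, complete data): 1 + 1 − 2·rho = 2(1 − rho)
- 12-week score adjusted for baseline: 1 − rho²
- Ratio, change to adjusted: 2(1 − rho)/[(1 − rho)(1 + rho)] = 2/(1 + rho)

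**Step 3: power at 94 complete per arm.** The effective effect size is 0.53/sqrt(2(1 − rho)) for the interaction and 0.53/sqrt(1 − rho²) for the adjusted contrast, put into the step 1 formula. The one degree of freedom spent on the covariate is ignored.

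| rho | Effective d, interaction | Power, interaction | Effective d, adjusted | Power, adjusted | Variance ratio |
|---|---|---|---|---|---|
| 0.3 | 0.448 | 0.863 | 0.556 | 0.966 | 1.54 |
| 0.4 | 0.484 | 0.910 | 0.578 | 0.976 | 1.43 |
| 0.5 | 0.530 | 0.951 | 0.612 | 0.987 | 1.33 |
| 0.6 | 0.593 | 0.981 | 0.663 | 0.995 | 1.25 |
| 0.7 | 0.684 | 0.997 | 0.742 | 0.999 | 1.18 |

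At rho = 0.5 the factor 2(1 − rho) equals 1, so the interaction has exactly the power of the planned t test. Below 0.5 it has less, above 0.5 more. The adjusted contrast starts at 0.951 when rho = 0 and rises from there.

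**Step 4: effect of maximum likelihood.** The protocol keeps participants who have only a baseline score. With 113 randomised and 94 followed per arm, and dropout at random, the variance of the interaction per arm is (1 − rho²)/94 + (1 − rho)²/113. By the normal approximation, power is then 0.886, 0.926, 0.960 and 0.985 at rho 0.3, 0.4, 0.5 and 0.6. It is 0.944 at rho 0.45, so the 95% crossing moves to between 0.45 and 0.5. The gain is real but small.

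**Step 5: the other scaling of 0.53.** If 0.53 is standardised on the SD of change, the interaction has effective d = 0.53 and power 0.951 at every rho. The variance ratio 2/(1 + rho) is unaffected.

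**The case against.** The case on the other side is that a time-by-condition mixed model is a standard and valid analysis, and that contrast wording is often left to a statistical analysis plan, which is not shown here. In a trial that says it was sized for a differential impact against control, the interaction is the obvious efficacy test. This stands in part: the test is valid, and preferring baseline adjustment is a gain in efficiency, not the repair of an error. But the protocol has stated the model and its terms, so the choice is already made there, and a better one is available at no cost.

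The documents do not support several stronger readings that a reader might draw:
- *The trial is underpowered.* That needs rho below about 0.5 and 0.53 scaled by the 12-week SD. Neither is given, and at rho 0.6 or 0.7 the interaction exceeds the stated power.
- *There is no 12-week comparison.* With two time points, the interaction is itself a one-degree-of-freedom between-arm contrast to week 12. It is only not labelled as primary.
- *The secondary outcomes get a two-degree-of-freedom omnibus test.* This holds only if time is categorical, which the protocol does not say.
- *Three competing p-values for efficacy.* The time effect does not compare the arms.
- *Power is only 50 to 61%.* This is the condition main effect, which averages in a null baseline difference: 0.265/sqrt((1 + rho)/2) gives 0.61, 0.55 and 0.50 at rho 0.3, 0.5 and 0.7. The protocol nowhere makes it the efficacy test.
- *The analysis uses baseline worse than was planned for.* The powered t test uses no baseline at all; the loss is relative to adjustment.

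**Conclusion.** The point holds as a free improvement with one needed clarification. Section 2.4.2 does not designate its efficacy test, and the natural candidate for eASSIST has 1.54 to 1.18 times the variance of a baseline-adjusted 12-week contrast for rho from 0.3 to 0.7. The size of that ratio rests on equal SDs. The direction does not, because regression on baseline chooses the slope with the smallest residual variance, whereas a change score fixes it at 1.

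Whether the interaction misses the stated 95% power cannot be settled from the protocol. If 0.53 is on the 12-week SD, power at 94 complete per arm runs from 0.863 (rho 0.3) to 0.997 (rho 0.7), slightly higher at the low end under maximum likelihood. If 0.53 is on the SD of change, there is no shortfall. With 0.53 on the 12-week SD, as the powered comparison of means implies, the adjusted contrast keeps at least 0.951 whatever rho is. That removes the dependence on a correlation the protocol does not give.

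**What to change.** In section 2.4.2, name one primary test: the between-arm difference in 12-week eASSIST score adjusted for the baseline score, by ANCOVA or by the mixed model with baseline means constrained equal across arms. Use the same baseline-adjusted 12-week contrast for days of stimulant use and DASS-21. In the Sample size estimate section, state which SD the 0.53 refers to.

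Optionally, use the 6-week data, such as days of stimulant use, as auxiliary information for missing 12-week eASSIST scores.

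The cost is a few sentences of analysis wording, best settled before outcomes are compared by arm. No new data, visits or participants are needed.
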